6.5.4 Dose modifications

For participants who do not tolerate the protocol-specified dosing schedule, dose interruptions are required to allow participants to continue the study treatment.

Dose modifications for sabatolimab

Dose modifications for sabatolimab will be done according to ASCO guidelines for management of immune-related AEs including hematological AEs. (Brahmer et al 2018)

Additionally, the guidance indicated in Table 6-3 below, provides instructions for infusion reaction, immune-related adverse events not covered by ASCO guidelines and a general guideline for non-hematologic non-immune-related toxicities that are clinically significant per investigator judgement and possibly attributable to the investigational drug. This general guideline will not apply in case of non-hematologic non-immune-related toxicities that are attributable to azacitidine and its complications.

Deviations to dose interruptions, reductions and/or permanent discontinuations outlined in Table 6-3 are not allowed.

Administration of sabatolimab may be delayed due to toxicities. A scheduled dose may be delayed within a cycle by up to 14 days. If a dose cannot be administered within the planned window within the cycle, then the dose should be skipped. Next scheduled dosing may resume once the adverse event has resolved to \leq Grade 1 or baseline per the next planned treatment cycle. Dose reductions for sabatolimab are not allowed.

Overall, for adverse events of potential immune-related etiology (other than GvHD) that do not recover to \leq Grade 1 or baseline and be maintained at a dose of immunosuppression of \leq 10 mg/day prednisone or equivalent (or as indicated in Table 6-3 within 12 weeks after initiation of immunosuppressive therapy), sabatolimab must be permanently discontinued.

For acute and/or chronic GvHD, refer to Table 6-4 for study treatment interruption, reinitiation and/or permanent discontinuation.

Dose interruption at the start of a new treatment cycle (Combination cohort)

In participants who have Grade 4 neutropenia and/or Grade 4 thrombocytopenia dosing of azacitidine should be interrupted until resolution to \leq Grade 2. Sabatolimab should not be administered during azacitidine dose interruption. After resolution, dosing of azacitidine may be resumed on the same day. The first day dosing is resumed will be considered as D1 of the new treatment cycle and sabatolimab will be administered on Day 5 of the new cycle. In participants who achieved CRi or MLFS, azacitidine has been permanently discontinued, remain on sabatolimab, but have Grade 4 neutropenia and/or Grade 4 thrombocytopenia; dosing of sabatolimab should be interrupted until resolution to \leq Grade 2. The first day dosing with sabatolimab is resumed will be considered D5 of the new cycle.

For study treatment interruption for acute and/or chronic GvHD, refer to Table 6-4.

Table 6-3 Criteria for dose interruption, re-initiation and discontinuation of sabatolimab due to adverse drugs reactions

	ilmab due to adverse drugs reactions
Worst Toxicity Grade (CTCAE v5.0)	Recommended Dose Modifications
Infusion Reaction	
Grade 1	Decrease infusion rate until recovery
Grade 2	Stop infusion
	Before restarting – pre-medicate according to local institutional guidelines.
	Restart infusion at 50% of previous rate under continuous observation. Ensure that there is a minimum observation period of 1 hour prior to restarting the infusion(s)If the AE recurs at the reinitiated slow rate of infusion, and despite oral pre-medication*, then discontinue MBG453
Grade 3	Stop infusion
	If the AE resolves to ≤ Grade 1 within 72hrs:
	· At next scheduled treatment visit, pre-medicate according to local institutional guidelines.
	· Restart infusion at 50% of previous rate under continuous observation. Ensure that there is a minimum observation period of 1 hour
	· If the AE recurs despite slow rate of infusion and pre-medication*, then discontinue sabatolimab
	If the AE does not resolve to ≤ Grade 1 within 72hrs:
	· Discontinue sabatolimab
Grade 4	Discontinue sabatolimab
Guidelines for the mana	ght to be immune-related and not covered in the ASCO gement of immune-related adverse events in participants treated t inhibitor therapy (Brahmer et al 2018)
Grade 1	Continue treatment with sabatolimab
Grade 2 or Grade 3 ≤ 7 days	Delay treatment with sabatolimab until resolved to ≤ Grade 1 or baseline
Grade 3 lasting > 7 days	1st and 2nd occurrence:
but < 21 days	Delay study treatment until resolved to ≤ Grade 1 or baseline
	3rd occurrence:
	Discontinue study treatment
Grade 3 lasting ≥ 21 days Or Grade 4	Discontinue study treatment
Dermatological toxicities	
Grade 1	Maintain sabatolimab. Use topical steroids, antihistamines, topical emollients.
Grade 2	Consider interrupting sabatolimab.
	Use topical or oral steroids, antihistamines.
	If sabatolimab is interrupted and resolution to ≤ Grade 1, restart sabatolimab.
Grade 3 or 4	Interrupt sabatolimab.
	Manage per institutional practice.
	After resolution to ≤ Grade 1, consider restarting sabatolimab.
Bullous dermatitis	Grade 1, 2, and 3: Interrupt sabatolimab. Consult with dermatologist

Worst Toxicity Grade (CTCAE v5.0)	Recommended Dose Modifications
	Grade 4: Permanently discontinue sabatolimab.
Stevens-Johnson syndrome (SJS) or Lyell syndrome/toxic epidermal necrolysis (TEN)	Permanently discontinue sabatolimab.
	non-immune related adverse events clinically significant** and the investigational drug (NCI CTCAE v5.0)
(The guideline does not a AML including its complic	pply to for toxicities attributable to azacitidine or the underlying ations)
Grade 1 and Grade 2 tolerable	Continue treatment with sabatolimab
Grade 2 intolerable and	1st or 2nd occurrence:
Grade 3	· Interrupt sabatolimab until toxicity recovers to ≤ Grade 1 or baseline
	· Once recovered to ≤ Grade 1 or baseline restart sabatolimab at the same dose level and schedule
	AE resolution to ≤ Grade 1 or baseline must occur within a maximum period of 56 days since interruption, otherwise sabatolimab must be permanently discontinued.
	3rd occurrence:
	· Permanently discontinue sabatolimab
Grade 4	Discontinue sabatolimab

All dose modifications should be based on the available information and worst preceding toxicity *Prophylaxis regimens will include both paracetamol/acetaminophen and an antihistamine.

Dose modifications for azacitidine (Combination cohort)

If azacitidine is deemed by the investigator to possibly have contributed to an observed adverse event, the dose or schedule of azacitidine may be modified within a cycle and/or for subsequent cycles, or temporarily interrupted, or permanently discontinued.

Permanent discontinuation of sabatolimab and azacitidine (Combination cohort)

If the study treatment (sabatolimab + azacitidine) is interrupted for toxicities other than GvHD and the start of the subsequent study treatment cycle is delayed for more than 28 consecutive days from the intended start date of cycle (Day 29 of the previous cycle) the participant should be discontinued from study treatment. For permanent discontinuation of study treatment due to acute and/or chronic GvHD, refer to Table 6-4.

Permanent discontinuation of only one component sabatolimab (or azacitidine - Combination cohort)

If **one component only** of the study treatment (azacitidine or sabatolimab) is discontinued for toxicities (other than GvHD), then the treatment may continue with the other component of study treatment alone (sabatolimab alone or azacitidine alone) as long as the participant benefits per investigator's judgement.

These dose changes must be recorded on the appropriate CRF.

^{**}Per investigator judgement

Table 6-4 Criteria for dose interruption, re-initiation and discontinuation of study treatment due to GvHD

	y treatment due to G	T	Diagontino ()				
	Interrupt study treatment [£] (sabatoli mab monotherapy or in combination with azacitidine)	Resume study treatment (sabatolimab monotherapy or in combination with azacitidine)	Discontinue study treatment permanently (sabatolimab monotherapy or in combination with azacitidine)				
Acute GvHD (aGvHD)	New onset grade II requiring systemic therapy New onset grade III Baseline grade I or II worsening to grade III III III III III III III II	 If aGvHD improved to ≤ grade I or to baseline prior to starting study treatment within ≤ 8 weeks of observation from onset or exacerbation of aGvHD The following are allowed at time of resumption of study treatment: Topical, nonabsorbable or inhaled steroids Systemic doses of steroids ≤ 10 mg prednisone or equivalent Tacrolimus with trough levels <5 ng/mL OR CSA with trough levels <200 ng/mL (indicating continuous IST taper) 	 Grade IV aGvHD Recurrence or exacerbation of aGvHD to ≥ grade III after resuming study treatment Steroid-refractory aGvHD No improvement to ≤ grade I or to baseline prior to starting study treatment after 8 weeks of observation from onset or exacerbation of aGvHD 				
Chronic GvHD (cGvHD)	New onset moderate cGvHD ONLY if requires systemic therapy with > 5 mg prednisone or equivalent	If cGvHD improved to ≤ mild cGvHD or to baseline prior to starting study treatment within ≤ 8 weeks of observation from onset or exacerbation of aGvHD	Severe cGvHD Moderate cGvHD of the lungs Baseline moderate cGvHD worsening to severe cGvHD Recurrence or exacerbation of cGvHD to				

Interrupt study treatment [£] (sab mab monothera or in combinati with azacitidine	atoli treatment apy (sabatolimab ion monotherapy or in	Discontinue study treatment permanently (sabatolimab monotherapy or in combination with azacitidine)
	 The followings are allowed at time of resumption of study treatment: Topical, non-absorbable or inhaled steroids Systemic doses of steroids ≤ 10 mg prednisone or equivalent Tacrolimus with trough levels <5 ng/mL OR CSA with trough levels <200 ng/mL (indicating continuous IST taper) 	moderate cGvHD that requires systemic therapy with > 5 mg prednisone or equivalent; severe cGvHD; or moderate cGvHD of the lung after resuming study treatment Steroid refractory cGvHD No improvement to ≤ mild or to baseline prior to starting study treatment after 8 weeks of observation from onset or exacerbation of cGvHD

[£]Treatment of GvHD at the discretion of the treating investigator

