6.1 Study treatment

In this study, the term "investigational drug" refers to the Novartis study drug, sabatolimab (MBG453).

The term "study treatment" refers to the combination of study drugs: sabatolimab plus azacitidine or sabatolimab alone.

All doses prescribed, dispensed to the participant and all dose changes during the study including the reason must be recorded on the appropriate electronic case report form (eCRF) page.

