6.5.5.2 Follow-up for immune -related AEs

The emergence of Immune-Related AE (irAE) may be anticipated based on general experience in clinical studies with similar class of compounds that block the negative immune regulators.

An irAE is any clinically significant AE affecting any organ that is associated with study drug exposure, is consistent with an immune-mediated mechanism, and where alternative explanations have been investigated and ruled out or are considered to be unlikely. Serologic, histologic and immunological assessments should be performed as deemed appropriate by the Investigator, to verify the immune related nature of the AE. An empiric trial of corticosteroids may also contribute to understanding the etiology of a potential irAE.

However, in the post-aHSCT setting, acute and chronic GvHD manifestations may overlap and be challenging to distinguish from irAEs [eg, skin rash, liver (hyperbilirubinemia, cholestasis, transaminitis), diarrhea, pneumonitis, etc.].

All participants with signs or symptoms of irAEs not attributed to acute or chronic GvHD should be monitored and managed following the ASCO Guidelines for the management of immune-related adverse events in participants treated with immune checkpoint inhibitor therapy (Brahmer et al 2018). For irAEs not covered by ASCO guidelines, please refer to Table 6-3.

In case of a suspected irAE not attributed to acute or chronic GvHD, the relevant immunological assessments (e.g. rheumatoid factor, anti-DNA Ab, etc.) should be performed. In case of a toxicity suspected to be a cytokine release syndrome, the cytokine assessments outlined in Table 8-9 must be performed.

Participants should be monitored carefully for any skin toxicity or mucositis and study treatment should be discontinued for any suspected case of SJS/TEN.

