Quantitative data (e.g., age, body weight) will be summarized by appropriate descriptive statistics (e.g. mean, standard deviation, median, 25th and 75th percentiles, minimum, and maximum).

General definitions

"Investigational drug" refers to sabatolimab.

"Study treatment" refers to the combination of sabatolimab plus azacitidine or sabatolimab alone in the monotherapy cohorts.

"Study treatment component" or "study drug" refers to sabatolimab or azacitidine.

Other general definitions are detailed in Appendix Section 5.1.

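### For SJS/TEN in the combination cohort, Table 6-3 stops sabatolimab alone while Section 6.5.5.2 stops both drugs; the immune-related rows of Table 6-3 leave the same question open

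*Protocol*

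**What the plan says.** Protocol Section 6.1 says that the term *study treatment* "refers to the combination of study drugs: sabatolimab plus azacitidine or sabatolimab alone". SAP Section 2.1 uses the same definition ("refers to the combination of sabatolimab plus azacitidine or sabatolimab alone in the monotherapy cohorts") and has separate terms for a single drug. In Cohort 3, an instruction about study treatment is therefore an instruction about both drugs.

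Table 6-3 is titled "Criteria for dose interruption, re-initiation and discontinuation of sabatolimab due to adverse drugs reactions". Within it:

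- For immune-related events that the ASCO guideline does not cover, Grade 2, or Grade 3 of at most 7 days, carries "Delay treatment with sabatolimab until resolved to ≤ Grade 1 or baseline".
- In the same block, the first and second occurrence of Grade 3 lasting more than 7 but under 21 days carries "Delay study treatment until resolved to ≤ Grade 1 or baseline". A third occurrence, Grade 3 of 21 days or more, and Grade 4 carry "Discontinue study treatment".
- For SJS/TEN, sabatolimab is stopped permanently and azacitidine is not mentioned.

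Section 6.5.5.2 covers SJS/TEN as well: "study treatment should be discontinued for any suspected case of SJS/TEN".

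If one component only is stopped for toxicity other than GvHD, Section 6.5.4 says "then the treatment may continue with the other component of study treatment alone (sabatolimab alone or azacitidine alone"), provided the investigator judges that the participant benefits. Section 3 says much the same. Section 6.5.4 also rules out deviations from Table 6-3.

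**The concern.** The protocol defines its terms, so moving from *sabatolimab* to *study treatment* changes the instruction in Cohort 3. In the monotherapy cohorts the two terms mean the same drug and no conflict arises.

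At stake is which regimen a Cohort 3 participant receives after a serious event. Sections 1.1 and 4.3 present azacitidine as an antileukemic agent that also inhibits GvHD, so being left on azacitidine and being left on nothing are materially different. Two sites could act differently on the same event, each citing the protocol. A site that continued azacitidine under Table 6-3 and the one-component rule would be out of line with Section 6.5.5.2.

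**Working it through.** The check is a comparison of text. Each instruction is read for Cohort 3 using the Section 6.1 definition.

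| Event | Place in protocol | Drug(s) stopped or held |
|---|---|---|
| SJS/TEN | Table 6-3 | sabatolimab |
| SJS/TEN, any suspected case | Section 6.5.5.2 | both |
| Immune-related, outside ASCO: Grade 2, or Grade 3 ≤ 7 days | Table 6-3 | sabatolimab (delay) |
| Same block: Grade 3 > 7 and < 21 days, 1st and 2nd occurrence | Table 6-3 | both (delay) |
| Same block: 3rd occurrence, Grade 3 ≥ 21 days, or Grade 4 | Table 6-3 | both (stop) |
| Immune-related other than GvHD, not recovering within 12 weeks of starting immunosuppression | Section 6.5.4 text | sabatolimab (stop) |
| GvHD | Table 6-4 | both, stated in the column headings |

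**SJS/TEN.** A confirmed case has also been a suspected case, so it falls under both of the first two rows. Take each possible action in turn:

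- Stop sabatolimab and continue azacitidine: this satisfies Table 6-3 and is permitted by the one-component rule, but it breaches Section 6.5.5.2.
- Stop both: this satisfies Section 6.5.5.2 and does not breach Table 6-3.

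An action allowed by one pair of passages is ruled out by another passage. That is a contradiction about a single named event.

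**Immune-related rows.** These rows cover different severities, so they do not contradict each other. Three features make the intent unclear. The table's title limits it to sabatolimab. The Section 6.5.4 text on immune-related events that fail to recover names sabatolimab alone. Table 6-4, where both drugs are meant, says so in each action column, and Table 6-3 has no such wording.

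**Consequence of the reading.** Section 6.5.4 ends both drugs when the combination is interrupted for non-GvHD toxicity and the next cycle starts more than 28 days late. In Cohort 3 a cycle starts with azacitidine (Protocol Section 8; SAP Section 5.1). If only sabatolimab is held, azacitidine can still start the next cycle on time, a missed sabatolimab dose is skipped, and the 28-day rule need not come into play. If both are held, the cycle start itself is delayed and the rule can apply. The choice of term can therefore decide whether a hold becomes permanent loss of both drugs.

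**Numerical check.** For success at 11 or more of 20, the exact binomial tail is P(X ≥ 11 | p = 0.30) = 0.0171 and P(X ≥ 11 | p = 0.60) = 0.7553. These match the stated 1.7% and 75.5% (Protocol Section 12.8.1). Neither figure depends on which drug is stopped.

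**The case against.** The strongest reply has four parts.

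1. *The SJS/TEN passages can be followed together.* Table 6-3 speaks only for sabatolimab and does not tell anyone to continue azacitidine, so stopping both complies throughout. This is true, but it does not resolve the matter. Continuing azacitidine also complies with Table 6-3 and the one-component rule, and only Section 6.5.5.2 forbids it.

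2. *The switch in the immune-related rows is graded escalation.* Holding one drug at lower severity and both at higher severity is coherent, and the Section 6.5.4 text has its own trigger and refers to Table 6-3. This largely stands. The rows are supporting evidence of unclear drafting and do not prove a contradiction.

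3. *Discretion already covers azacitidine.* Section 6.5.4 lets the investigator modify or stop azacitidine if it may have contributed, and continuing the other component is permissive. So divergence between participants is possible, not certain. Discretion does not help, however, where one passage permits a choice and another removes it.

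4. *Recruitment has stopped.* The SAP (Sections 1 and 2.1) records the halt and the termination of the programme. This reduces the prospective benefit. The point still matters for reviewing compliance of any treated Cohort 3 participant and for reuse of the text.

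A reader might also infer more than the documents support. Table 12-3 shows 10/20 failing (posterior probability 0.974) and 11/20 succeeding (0.991), so it is tempting to say that this wording could reverse the Cohort 3 conclusion. Any single changed outcome from any cause moves that boundary. Nothing in the documents estimates how often these events would occur or links them to relapse, and the primary efficacy estimand takes outcomes into account regardless of interruption or discontinuation. It is equally tempting to say that exposure could not be derived. But doses and dose changes are recorded for both drugs (Protocol Sections 6.1 and 6.6.1), and the SAP summarises exposure and dose changes by drug (Sections 2.4.1 and 5.1).

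**Conclusion.** The protocol is wrong as written: it contradicts itself for SJS/TEN in Cohort 3. One passage, read with the one-component rule, allows azacitidine to continue; another stops it. The immune-related rows of Table 6-3 add an ambiguity that may be intended but is not stated, and that bears on the 28-day rule.

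The issue is confined to Cohort 3 (20 planned participants) and to what those participants receive. It does not touch the success threshold, type I error, power or the classification of response. Its frequency cannot be estimated from the documents. The conclusion rests on reading *study treatment* as defined in Section 6.1.

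The infusion-reaction and anaphylaxis rules in Section 6.2.1 also use different terms, but they concern separately named events. They are worth a wording check and are not evidence of contradiction. No view is taken on which clinical instruction is right.

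**What to change.** The sponsor's clinical team should reconcile Table 6-3, Section 6.5.4 and Section 6.5.5.2:

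- In each row or sentence, name the drug or drugs affected (sabatolimab, azacitidine, or both) in place of *study treatment*.
- Give SJS/TEN one instruction, used in both places.
- If the immune-related rows are meant to move from one drug to both as severity rises, say so and adjust the table title.
- Cross-refer from Table 6-3 to the one-component rule and to the 28-day rule, stating when each applies.
- Check the terms in Section 6.2.1 at the same time.

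The cost is protocol wording and a letter to sites. No new data collection or change to the eCRF is needed.

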6.5.5 Follow-up for toxicities

Participants whose treatment is interrupted or permanently discontinued due to an AE or clinically significant laboratory value, must be followed-up at least once a week (or more frequently if required by institutional practices, or if clinically indicated) for 4 weeks, and subsequently at approximately 4-week intervals, until resolution or stabilization of the event, whichever comes first. Appropriate clinical experts should be consulted as deemed necessary.

All participants in Safety Run-in, expansion monotherapy, and adolescent cohorts must be followed up for AEs (including but not limited to acute and chronic GvHD, irAEs and SAEs) for 150 days following the last dose of sabatolimab.

All participants in combination cohort must be followed up for AEs (including but not limited to acute and chronic GvHD, irAEs and SAEs) for 30 days following the last dose of azacitidine and 150 days following the last dose of sabatolimab, whichever is later.

In addition to the instructions provided in this section, please refer to Section 16.3 (Appendix 3) for further guidance on renal alert criteria, actions and events follow up.

6.5.5.1 Follow up on potential drug-induced liver injury (DILI) cases

Guidelines for follow-up on potential DILI cases are described in Table 6-5 and Table 6-6.

Table 6-5 Follow-up of abnormal liver chemistry results

ALT	TBL	Liver Symptoms	Action		
ALT increase without	bilirubin increase:				
If normal at baseline: ALT > 3 x ULN If elevated at	Normal For participants with Gilbert's syndrome:	None	No change to study treatment Measure alanine		
baseline: ALT > 2 x baseline or > 200 U/L (whichever occurs first)	No change in baseline TBL		(ALT), aspartate aminotransferase (AST), alkaline phosphatase (ALP), gamma-glutamyl transferase (GGT), TBIL, INR, albumin, lactate dehydrogenase (LDH), CK, and glutamate dehydrogenase (GLDH) in 48-72 hours. - Follow-up for symptoms		
If normal at baseline:	Normal	None	- Interrupt study drug		
ALT > 5 x ULN for more than two weeks	For participants with Gilbert's syndrome:		- Measure ALT, AST, ALP, GGT, TBIL, INR,		
If elevated at baseline:	No change in baseline TBL		albumin, LDH, CK, and GLDH in 48-72 hours.		
ALT > 3 x baseline or > 300 U/L (whichever occurs first) for more than two weeks			Follow-up for symptoms.Initiate close		
If normal at baseline: ALT > 8 x ULN	Normal	None	monitoring and workup for competing etiologies.		
ALT increase with bili	rubin increase:		- Study drug can be		
If normal at baseline: ALT > 3 x ULN	TBL > 2 x ULN (or INR > 1.5)	None	restarted only if another etiology is		
If elevated at baseline:	For participants with Gilbert's syndrome:		identified, and liver enzymes return to baseline.		
ALT > 2 x baseline or > 200 U/L (whichever occurs first)	Doubling of direct bilirubin		Basoniio.		
If normal at baseline:	Normal or elevated	Severe fatigue,			
ALT > 3 x ULN		nausea, vomiting, right upper quadrant			
If elevated at baseline:		pain			
ALT > 2 x baseline or > 200 U/L (whichever occurs first)					

Table 6-6 Action required for isolated total bilirubin elevation

Abnormality	Action required
Any elevation > ULN	Fractionate bilirubin, evaluate for cholestatic liver injury (ALP) or alternative causes of bilirubin elevation. Treat alternative causes according to local institutional guidelines
Grade 2 (>1.5 - 3.0 ULN)	Maintain treatment. Repeat LFTs within 48-72 hours, then monitor LFTs weekly until resolution to ≤ Grade 1 or to baseline
Grade 3 (>3.0 – 10 ULN)	Interrupt treatment. Repeat LFTs within 48-72 hours, then monitor LFTs weekly until resolution to ≤ Grade 1 or to baseline
Grade 4 (> 10 x ULN)	Discontinue study treatment

If abnormalities are confirmed, close observation and follow-up are required:

- 1. A detailed assessment of potential treatment emergent GvHD of liver (acute or chronic) should be performed by the Investigator
- 2. A detailed history, including relevant information, such as cardiac disease, history of any pre-existing liver conditions or risk factors, blood transfusions, IV drug abuse, travel, work, alcohol intake, and full clinical examination for evidence of acute or chronic liver disease, cardiac disease and infection etc. should be performed.
- 3. Review of concomitant medications, including nonprescription medications and herbal and dietary supplement preparations, alcohol use, recreational drug use, special diets, and chemicals exposed to within one month of the onset of the liver injury.
- 4. Further testing for acute hepatitis A, B, C or E infection and liver imaging (e.g. biliary tract) may be warranted.
- 5. Obtain an unscheduled PK sample, as close as possible to last dose of study treatment.

Additional testing for other hepatotropic viral infection (EBV or HSV), autoimmune hepatitis or liver biopsy may be considered as clinically indicated or after consultation with specialist/hepatologist.

